2.0 TRIAL DESIGN

2.1 Trial Design

This study is a small Phase II clinical trial designed as a single-arm two-stage study with Dexamethasone dose escalation cohorts (4mg BID on days 1-7, 1-10 or 1-13). The trial will include FLT-PET and FDG-PET imaging to measure tumor senescence to Dexamethasone and treatment response respectively, and also blood analysis for SASP and markers of immune activation. This study is to assess whether senescence induced by oral dexamethasone resensitizes NSCLC patients to intravenous pembrolizumab.

We will use a single arm phase II two-stage design with 3 Dex cohorts (4 mg bid, on Days 1-7, 1-10 and 1-14) to achieve 80% power at a 1-sided alpha 10% level. Each cohort will consist of 5 patients. On the basis of Simon's optimal design, the first cohort will be accrued in the first stage. If there are 3 or more "responses" occur among this cohort, 7 additional patients will be accrued and treated with the same Dex dose for a total of 12 patients; if 7 or more respond at this dose level, we will add 9 more patients for a total of 21 patients (with 20% drop out, n = 31). If no response is noted on FLTPET, 2nd cohort will open up with a 10 day fixed dose Dex and so on as depicted in Schema.

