11.0 STATISTICAL ANALYSIS PLAN

11.1 Statistical Design (see page 10 for Schema)

In the first stage, three DEX escalation cohorts will be evaluated sequentially from Cohort A to Cohort C until two or more patients have the FLT-PET response (i.e., \geq 30% reduction in FLT-PET uptake in at least one target lesion) and, otherwise, the trial will be terminated due to futility. When a lead-in cohort has two or more FLT-PET responses, this lead-in cohort will be considered the optimal DEX duration and the primary endpoint will be evaluated in the following second and third stages using this optimal DEX duration. That is, after the optimal DEX duration is decided in the first stage, six additional patients will be enrolled in the second stage with the same DEX duration as the associated cohort. If four or less patients respond among 11 patients, the trial will be terminated. Otherwise, 10 additional patients will be enrolled in the third stage. The null hypothesis ($p_0 = 30\%$) will be rejected if 10 or more FLT-PET responses are observed in 21 patients. This design yields a 1-sided type I error rate of 5% and power of 80% when the true FLT-PET response rate is 60% (i.e., $p_1 = 60\%$). The minimum sample size will be 11 patients when Cohort A becomes the optimal duration and the trial is terminated at the end of the second stage. The maximum sample size will be 31 patients when Cohort C becomes the optimal duration and the patients are enrolled into the third stage.

We will also explore the associations between the FLT-PET response and the changes in senescence associated secretory proteins (SASP) and lymphocyte, phenotypic and functional markers (LPFM), (ii) monitor the changes and trajectories in SASP and LPFM, and (iii) explore the association between the FLT-PET response and GR expression at cycle 0. The expression levels of SASP and LPFM/GR will be measured using plasma and tissue samples,

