11.2 Sample Size Justification

The clinical trial is a single arm phase II intervention trial in Veterans as second line therapy, after progression on initial chemo-immunotherapy or immunotherapy for NSCLC. The enrolled patient will be in the study for 3 months and will then be followed for up to 2 years. We currently see at least 2-3 patients per month who will satisfy eligibility criteria and thus

the enrollment will be completed within 2 years (min 21 and max 39 patients). A sample size of 21 patients will not be powered for all the comparisons. But the data information obtained from this study will provide us preliminary information to design a more definitive study

The sample size was justified based on the primary objective. The FLT-PET response will be evaluated using a Phase II single-arm three-stage design with three lead-in efficacy (futility) cohorts. The sample size was estimated to achieve 80% power with a 1-sided 5% type I error rate and the estimated sample size is varied according to the selected optimal duration, which ranges from 21 patients (when Cohort A is optimal) to 31 patients (when Cohort C is optimal). Considering up to 20% drop-out rate, the required sample size will be between 21 patients (i.e., no drop-out with Cohort A as the optimal duration) and 39 patients (i.e., 20% drop-out with Cohort C as the optimal duration). For the secondary objective, the use of 21 patients (when the FLT-PET response trial enters the third stage) will allow us to achieve 87% power when the true ORR is 33% with a 1-sided type I error rate of 5%. We expect that the accrual rate will be at least 35 eligible and evaluable patients per year.

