11.3 Population for Analysis

Intent-to-Treat Population: All patients consented and enrolled in the trial.

Evaluable Population: Only those patients who have received at least one cycle of therapy with dexamethasone and pembrolizumab will be considered evaluable.

Safety Evaluable Population: Patients who receive any treatment on protocol will be considered evaluable for safety.

11.4 Analysis of Primary Objective: The primary objective is to identify the smallest duration of fixed dose Dex that results in a >30% reduction in FLTPET. We will utilize a 2 stage design with 3 cohorts (see Statistical schema). The hypothesis is that the true “response” in FLTPET (reduction in FLTPET by >30% following Dex in at least 1 target lesion) will be 60% ($p_1=60$) vs. p_0 30% (based on preliminary data that chemotherapy such as docetaxel results in irreversible cell cycle arrest as measured by S-phase surrogate on FLT-PET (39)).

Secondarily, we will compare FLTPET “response” to GR expression and generation of SASP and immune effector cells. We will also track the trend in immune effector cell response at later time points (cycle 2 and 3) to test contributory effects of pembrolizumab and Dex on the immune phenotype in the blood.

11.5 Analysis of Secondary Objectives The secondary objective is to establish that the true ORR of Dex followed by pembrolizumab will be at least 33% ($p_1 = 0.33$) vs. docetaxel treatment (as the historical control) whose ORR is

$\leq 7\%$ ($p_0 = 0.07$). The ORR will be assessed at a 12 week FDG PET scan. The required sample size for both lead-in FLTPET response and phase 2 studies will range 21 to 31 patients. As secondary objectives, we will explore associations of the change in FLT-PET with ORR assessed by FDG-PET, level of plasma SASP, and immune cell activation. The change in FLT-PET will be compared by ORR using an unpaired t-test and the associations with the level of plasma SASP and immune cell activation will be examined by a correlation analysis. The power is not formally justified because these are exploratory

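### The 80% power in Sections 11.1 and 11.2 holds for a dexamethasone duration once it is opened; it is not the chance that the trial reaches and declares a longer duration

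*Combined protocol and SAP*

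**What the plan says.** Section 11.1 describes a sequential lead-in: "three DEX escalation cohorts will be evaluated sequentially from Cohort A to Cohort C until two or more patients have the FLT-PET response". Section 2.1 gives the cohort size: "Each cohort will consist of 5 patients". When a cohort passes, "this lead-in cohort will be considered the optimal DEX duration", and the later stages use that duration only: "six additional patients will be enrolled in the second stage with the same DEX duration as the associated cohort". The next rule is "If four or less patients respond among 11 patients, the trial will be terminated". With five or more responders at that look, the plan goes on to the last group: "10 additional patients will be enrolled in the third stage". The 30% null is rejected with 10 or more responses in 21. Section 11.1 states a one-sided type I error of 5% and 80% power at a true rate of 60%.

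Section 11.2 repeats the 80% and ties it to a sample size "which ranges from 21 patients (when Cohort A is optimal) to 31 patients (when Cohort C is optimal". Section 11.4 states the aim: "The primary objective is to identify the smallest duration of fixed dose Dex that results in a >30% reduction in FLTPET".

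Section 2.1 describes the screen differently. It continues with 3 or more responses in the first cohort, then looks for 7 or more of 12, uses a one-sided alpha of 10%, and opens the second cohort if there is no response.

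**The concern.** Duration is the one factor that the plan varies on purpose: Section 4.2.2 sets 7, 10 and 13 days. The plan seeks the shortest duration that works, but a 5-patient screen decides which duration is tested. A duration with a true rate equal to the null passes that screen almost half the time. It is then called optimal, and the longer courses are closed. If it later fails, the trial ends with those courses never given.

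Two things are at stake. A reader of Section 11.2 may take 80% as the chance of a positive trial whichever duration is the first to work. And because Section 11 does not say how far a stop at 11 or a failure at 21 reaches, a negative result at a short duration could be read as covering durations that were not opened.

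**Working it through.** **Inputs.** From Section 11.1: pass the lead-in with ≥2 of 5, continue with ≥5 of 11, reject with ≥10 of 21; p0 = 30%, p1 = 60%. Cohort size 5 is from Section 2.1. Cohorts A, B and C are taken to be the 7-, 10- and 13-day cohorts of Section 6.1.1. There is no return to another duration after selection; the stated maximum of 31 = 5 + 5 + 21 fits only that reading.

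**Step 1: reproduce the plan's figure.** Exact binomial probabilities for one cohort followed through all three stages:

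| True rate | Pass ≥2/5 | and ≥5/11 | and ≥10/21 |
|---|---|---|---|
| 30% | 0.472 | 0.183 | 0.049 |
| 60% | 0.913 | 0.856 | 0.822 |

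This gives a type I error of 4.9% and power of 82.2%, in line with the stated 5% and 80%. Chaining all three cohorts at one common rate gives 8.9% and 90.0%, which does not match. The stated pair therefore describes a single duration.

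**Step 2: chain the cohorts.** Let s be the probability that a shorter course with true rate p passes the screen, so s = P(X ≥ 2 | n = 5, p). Then:

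- P(declare B), with A at p and B at 60%: (1 − s) × 0.822
- P(declare C), with A and B at p and C at 60%: (1 − s)² × 0.822

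| Shorter courses at | s | Declare B | Declare C |
|---|---|---|---|
| 5% | 0.023 | 80.3% | 78.5% |
| 10% | 0.081 | 75.5% | 69.3% |
| 20% | 0.263 | 60.6% | 44.7% |
| 30% (p0) | 0.472 | 43.4% | 22.9% |

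For the last row: 0.528 × 0.822 = 0.434 and 0.528² × 0.822 = 0.229. A simulation of 100,000 trials gave 43.3% and 22.8%.

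**Step 3: where the lost trials go when shorter courses are at 30%.**

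- A selected, then stopped at 11: 0.472 − 0.183 = 0.289.
- A selected, continued, then failed at 21: 0.183 − 0.049 = 0.134.
- Negative end on A, with B and C unopened: 0.289 + 0.134 = 0.423.
- Negative end on A or B, with C unopened: 0.423 × (1 + 0.528) = 0.646.

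**Step 4: the Section 2.1 rule.** With a true rate of 30%, P(≥3 of 5) = 0.163 and P(0 of 5) = 0.168. The remaining 1 − 0.163 − 0.168 = 0.669 is 1 or 2 responses, for which Section 2.1 gives no action. The chain in step 2 therefore cannot be repeated under Section 2.1 as written.

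**The case against.** **The 80% is not wrong.** A reader might infer a miscalculation. There is none: Section 11.1 conditions the figure on a true rate of 60%, and Section 11.2 says that the sample size varies with the selected duration. Power at a tested duration and the chance of reaching and declaring a later one are different quantities. This stands. What is missing is a statement of which one the 80% is.

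**The 30% scenario is demanding.** The null rate comes from docetaxel (Sections 1.0 and 11.4), so 43% and 23% require a too-short course to lower FLT uptake as often as chemotherapy does. At 5% the loss is small. Section 4.1.2 also reports S-phase suppression in 3 of 4 patients within 24 hours and a senescence phenotype within 7 days in cell lines. If 7 days is already at 60%, the stated power holds. This also stands, and it is why the result must be given as a range.

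**A stop on an ineffective duration as the most likely outcome.** A reader might infer this generally. It does not hold when B is the first effective duration: at 30% for A, declaring B (43.4%) is slightly more likely than a negative end on A (42.3%). It holds only when C alone works and A and B are at 30%.

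**An unanswerable objective.** This is also too strong. Testing upward and stopping at the first duration that passes is a natural way to look for the smallest one, and it gives an answer when A works or when an ineffective A is screened out.

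**Rates above the null.** With shorter courses at 40%, the chance of declaring B or C falls to 28% or 9%. But A is then itself declared effective in 24% of trials, and that is not a false rejection of p0. Those figures alone would mislead.

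**Reporting.** Section 11.1 uses the word futility only for the case where no lead-in cohort passes, and Section 11.2 calls the results preliminary. The documents do not show that a stop would be reported as failure of dexamethasone at every duration; they leave the scope unstated.

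**Conclusion.** The point holds as one about the scope of the stated power and the label given to the selected duration. Under Section 11.1, power is 82% for a duration once opened. The trial-level chance of declaring B runs from 80% down to 43%, and of declaring C from 79% down to 23%, as the true rate in shorter courses goes from 5% to 30%. At 30%, 42% of trials end negative on A with B and C unopened. If only C works, 65% end negative on A or B with C unopened. The aim in Section 11.4 may therefore go unanswered.

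The figures assume a true rate of 60% at the first effective duration, shorter courses at the rates shown, and Section 11.1 as the governing rule. Section 2.1 has different boundaries and a different trigger for the next cohort, and a 30% duration reaches its 3-of-5 threshold only 16% of the time. The two sections must be reconciled before any trial-level figure is final. The schema could not be seen, so the absence of a return to longer durations rests on the text and on the maximum of 31.

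**What to change.** 1. Reconcile Sections 2.1 and 11.1 on the screening threshold, the later boundaries, alpha and the rule for opening the next cohort. Recalculate the figures if the rule in Section 11.1 changes.
2. In Sections 11.1 and 11.2, say that 80% power applies to a single duration once it is opened. Add the trial-level figures for B and C over shorter-course rates of 5% to 30%.
3. Replace the label of optimal duration with: first duration to pass the lead-in screen.
4. State that a stop at 11, or a failure at 21, is a negative result for that duration only and is inconclusive for longer durations not opened.
5. Reword the aim in Section 11.4 to match.

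These power and scope changes (items 2 to 5) are wording only: no extra patients and no new boundaries. The cost is a less favourable stated power. Letting any failed cohort lead on to the next duration is not proposed. It would raise power to 78% for B and 74% for C with shorter courses at 30%, but overall type I error would be 1 − (1 − 0.049)³ = 14%, the maximum would exceed 31 patients, and new boundaries would be needed.

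### The 5% type I error in sections 11.1 and 11.2 is a per-duration figure (exact 4.9%). Over the three permitted lead-in cohorts it can reach 8.9%, no readable passage states which scope is meant, and section 2.1 gives a different level and rules.

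*Combined protocol and SAP*

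**What the plan says.** Section 11.1 sets out the primary test. In stage one, "three DEX escalation cohorts will be evaluated sequentially from Cohort A to Cohort C until two or more patients have the FLT-PET response". The first cohort to pass sets the dexamethasone duration, and "the primary endpoint will be evaluated in the following second and third stages using this optimal DEX duration". Six more patients make 11, and the trial stops at four or fewer responses. Otherwise ten more make 21, and the 30% null "will be rejected if 10 or more FLT-PET responses are observed in 21 patients". The error rate and power are then stated for this design as a whole: "This design yields a 1-sided type I error rate of 5% and power of 80% when the true FLT-PET response rate is 60" per cent. The next sentences give sample sizes that count all the lead-in cohorts (31 at most, through Cohort C).

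Section 11.2 says the endpoint will be "evaluated using a Phase II single-arm three-stage design with three lead-in efficacy (futility) cohorts", and that "The sample size was estimated to achieve 80% power with a 1-sided 5% type I error rate".

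Section 2.1 describes something else. The design is "to achieve 80% power at a 1-sided alpha 10% level", with thresholds of 3 of 5 and 7 of 12, then 9 more patients to reach 21. The second cohort opens when no FLT-PET response is seen in the first. Section 11.4 describes a two-stage design, whereas 11.2 describes three stages.

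**The concern.** A cohort that fails its lead-in is replaced by a fresh cohort at a longer duration, so the procedure has up to three routes to a positive primary result. An error rate calculated for one route does not bound the error of the whole procedure.

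The primary objective is not tied to one duration: section 3.1 covers 7, 10 or 13 days. A reader may therefore take 5% as the ceiling on a false-positive primary conclusion for the trial. Whether the design meets its intended level depends on two things the plan leaves open: whether the level applies per duration or trial-wide, and whether it is 5% (11.1, 11.2) or 10% (2.1).

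**Working it through.** **Inputs.** From 11.1: null rate 30%, alternative 60%; pass the lead-in with at least 2 responses; 6 more patients, continue with at least 5 of 11; 10 more patients, reject with at least 10 of 21. Lead-in size is 5: section 2.1 states "Each cohort will consist of 5 patients", and 11 − 6 = 5. Patients are taken as independent, and the passing cohort's own five patients count towards the 11 and the 21.

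**Step 1: one duration (the plan's own figures).** Let g be the probability of passing the lead-in and r the probability of passing all three thresholds.
- At 30%: g = 1 − 0.7⁵ − 5 × 0.3 × 0.7⁴ = 1 − 0.1681 − 0.3602 = 0.4718. Summing the binomial probabilities over all paths, the chance of also reaching 5/11 is 0.1831, and r = 0.0491.
- At 60%: g = 0.9130, the chance of also reaching 5/11 is 0.8565, and r = 0.8218.

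The stated 5% and 80% are thus reproduced as 4.9% and 82.2% for a single cohort.

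**Step 2: the whole procedure under 11.1.** The next cohort opens after 0 or 1 responses, with probability f = 1 − g. With a common rate, P(reject) = r(1 + f + f²).
- All at 30%: f = 0.5282 and f² = 0.2790, so 0.0491 × 1.8072 = 0.0888. By route: 4.9 points via A, 2.6 via B, 1.4 via C. A simulation of 400,000 trials gave 0.0892.
- All at 60%: f = 0.0870 and f² = 0.0076, so 0.8218 × 1.0946 = 0.8996.

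**Step 3: is 8.9% typical or a limit?** A grid over all null rates from 0 to 30% (step 1 point) puts the maximum at 30/30/30%. With unequal rates the sum is r_A + f_A·r_B + f_A·f_B·r_C.

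| True rates A/B/C | Trial-wide error |
|---|---|
| 30/30/30% | 8.9% |
| 25/30/30% | 6.2% |
| 27/27/27% | 4.8% |
| 20/25/30% | 3.7% (0.00284 + 0.01082 + 0.02292 = 0.03658) |
| 25/25/25% | 3.0% |

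**Step 4: the 2.1 transition rule.** Suppose the next cohort opens only after 0 of 5, a single response ends the trial, and the other 11.1 thresholds are kept. Then f is replaced by 0.7⁵ = 0.1681, and the total is 0.0491 × (1 + 0.1681 + 0.0282) = 0.0588. The trial-wide maximum is 5.9%, so most of the excess over 4.9% comes from the rule for opening the next cohort, and the two sections disagree on that rule.

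**Step 5: a final cut-off of 11/21, for comparison.** One duration: 2.2% error and 76.3% power. Trial-wide: 0.02186 × 1.8072 = 0.0395 (4.0%) at 30/30/30%, and 0.7626 × 1.0946 = 0.835 (83.5%) at 60/60/60%.

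**The case against.** The stated 5% and 80% reproduce from 11.1, so there is no slip in the calculation. Only one duration ever reaches the final test, and 11.1 ties the second and third stages to that duration, so a per-duration reading is natural. The 8.9% requires every duration to sit exactly on the null boundary; at 27% throughout the error is already below 5%. Sections 11.1 and 11.4 also refer to a schema that is not shown in our text and may settle the scope. Finally, 11.2 presents the trial as preliminary to a more definitive study.

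All of this stands as a limit on the point, but it does not remove it. The error rate is stated for the design immediately after all three cohorts are described, and it is repeated in 11.2 for the design with three lead-in cohorts. Neither place restricts it to one duration. The statements in 11.1 that no multiplicity correction will be made concern the exploratory marker associations, not the primary test.

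A reader might go further and infer that the power claim fails, because a weak early cohort can pass its lead-in and end the search before an effective duration is tried. The documents do not support calling that an error. The plan claims power only at a true rate of 60%, and at that common rate it is met both for one cohort and trial-wide. Mixed-rate scenarios would be a useful addition, not a correction.

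**Conclusion.** The point holds as one of unstated scope and conflicting specification. The 5% is right for one duration (4.9%) and is not a trial-wide bound: the maximum under 11.1 is 8.9%, reached when all three durations are at 30%. The power statement is sound (82.2% for one cohort, 90.0% trial-wide at a common 60%).

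Sections 2.1 and 11.1 cannot both be followed. They differ on alpha (10% against 5%), thresholds (3/5 and 7/12 against 2/5 and 5/11), the second and third stage sizes (7 and 9 against 6 and 10) and the trigger for the next cohort. Sections 11.4 and 11.2 differ on the number of stages.

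It would be tempting to conclude that the trial breaches its alpha and that the 10/21 rule must change. That does not follow: 10/21 satisfies both 5% per duration and 10% trial-wide, and fails only if 5% trial-wide is intended. These figures assume five patients per lead-in, independent patients, the 11.1 rules followed exactly, and nothing in the unseen schema that defines the scope.

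**What to change.** In 11.1 and 11.2, state that the rule has type I error 4.9% and power 82% for one duration. Add that the maximum trial-wide type I error is 8.9% (all durations at 30%), with 90% power if all durations are at 60%. Name one alpha level and say whether it applies per duration or trial-wide.

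Reconcile 2.1 (alpha, thresholds, stage sizes, rule for opening the next cohort) and 11.4 (number of stages) with 11.1. If the transition rule changes, recompute the trial-wide figure.

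For 5% per duration or 10% trial-wide, this is a text change only: no added patients and no change to the 10/21 rule. If 5% trial-wide is meant, the sponsor should either restate the level or consider 11/21. That cut-off needs no added patients and meets both stated figures on a trial-wide basis (4.0% and 83.5%), but one-cohort power falls to 76.3%.

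Optionally, report mixed-rate scenarios with correct and false rejections shown separately. With A and B at 30% and C at 60%, for example, the rejection probability is 30.4%, of which 7.5 points (4.9 via A, 2.6 via B) are false.

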3.0 OBJECTIVES

3.1 Primary Objective & Hypothesis

- (1) **Objective:** To determine the extent of senescence (as measured by change in FLT-Pet of single target lesion) induced by Dexamethasone administered for 7 or 10 or 13 days
- **Hypothesis:** The use of Dexamethasone in NSCLC patients who have progressed after first line immune/chemoimmunotherapy will result in senescence induction in 60% of patients, along with production of senescence associated secretory proteins (SASP) and immune activation.

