respectively. The secondary endpoints are the changes in SASP and LPFM expression levels between cycle 0 and cycle 1 as well as the expression level of GR at cycle 0. The association between the FLT-PET response and the changes in the expression levels of each of SASP and LPFM will be examined using logistic regression models. The expression levels of SASP and LPFM between cycle 0 and cycle 1 will be examined using a paired t-test, if needed, after data transformation (such as log or square root transformation). The association between the FLT-PET response and the GR expression level will be assessed using logistic regression models. The trajectories from cycle 0 to cycle 4 for the expression levels of each of SASP and LPFM will be examined to see if the expression levels increase monotonically across cycles. To do this, linear mixed-effects models will be used, if needed, after data transformation. In addition, in case that either Cohort B or C becomes the optimal duration, we will descriptively compare the changes in SASP and LPFM expression levels from cycle 0 to cycle 1 between lead-in cohorts. Because these are a discovery study to generate hypotheses, no multiple comparison correction will be made. However, if either the sample size is less than 12 patients or a level (i.e., response vs. non-response) has less than 5 events; all secondary objectives will be exploratory and will be summarized descriptively. All statistical analyses will be based on complete data and no missing data analysis will be performed.

The secondary objective is to assess the effect of DEX on pembrolizumab in terms of overall response rate (ORR), which is the primary endpoint. Based on our previous pre-clinical and clinical studies, we hypothesize that the true ORR of DEX followed by pembrolizumab will be at least 33% (i.e., $p_1 = 0.33$) vs. the historical control whose ORR is at most 7% (i.e., $p_0 = 0.07$). The ORR will be statistically evaluated when the FLT-PET response trial enters the third stage, where the number of patients with the selected optimal DEX duration will be 21. Otherwise, the ORR will be summarized descriptively. The null hypothesis ($p_0 = 7\%$) will be rejected if five or more responses are observed in 21 patients, which yields a 1-sided type I error rate of 5% and power of 87% when the true ORR is 33% (i.e., $p_1 = 33\%$).

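### FLT-PET is related to GR expression only through the yes/no response, although the change in uptake is measured; for SASP and immune markers two FLT analyses stand unreconciled

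*Combined protocol and SAP*

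**What the plan says.** **Response-based analyses.** Section 11.1 defines FLT-PET response as at least a 30% "reduction in FLT-PET uptake in at least one target lesion". It then states for GR: "The association between the FLT-PET response and the GR expression level will be assessed using logistic regression models". For the other markers, the association of response with "changes in the expression levels of each of SASP and LPFM will be examined using logistic regression models". Section 11.4 also compares FLT response with GR, SASP and immune effector cells, without naming a method.

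**Analyses of the change.** Section 11.5 says "we will explore associations of the change in FLT-PET with ORR assessed by FDG-PET, level of plasma SASP, and immune cell activation". The methods are "The change in FLT-PET will be compared by ORR using an unpaired t-test" and, for the blood markers, "associations with the level of plasma SASP and immune cell activation will be examined by a correlation analysis". Sections 2.1 and 4.2.3.1 describe the same t-test and correlation. GR is in none of these three places.

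**Objective and scale.** Secondary objective 3.2(4) asks how sensitivity to dexamethasone, judged on the pre- and post-treatment FLT scans, relates to GR by IHC; it gives no method. Section 3.1 describes senescence "as measured by change in FLT-Pet of single target lesion". Section 10.3 groups GR as low, intermediate or high, and section 4.2.3.1 also plans quantitative AQUA.

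**Fallback.** Under section 11.1 the secondary objectives become descriptive if there are fewer than 12 patients or if "a level (i.e., response vs. non-response) has less than 5 events".

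**The concern.** Each patient has a pre- and a post-dexamethasone scan, so the size of the FLT change is known. Reducing it to one side or the other of a 30% cut treats a 31% fall and an 80% fall as the same, and a 29% fall and a rise as the same. The protocol's own rationale is graded: section 4.2.2 describes the preclinical senescence effect as proportional to the intensity of GR expression. A yes/no outcome discards that gradient.

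For GR this is the only FLT analysis planned. For SASP and immune markers a continuous analysis exists, but it sits beside a logistic one for the same question with no order between them, so the choice can be made after the data are seen.

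Section 11.2 says the data are meant to inform a more definitive study. With 21 patients at the selected duration, an avoidable loss of information makes the GR result less useful for that purpose.

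**Working it through.** **Plan's own figure.** None exists for these associations: the plan gives no power, odds ratio or correlation. The sample size of 21 comes from the three-stage rule in section 11.1 (at least 2 of 5, more than 4 of 11, at least 10 of 21). Exact enumeration for a single cohort gives a type I error of 4.9% and power of 82.2%, in line with the stated 5% and 80%.

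**Inputs from the documents.** n = 21 at the selected duration (11.1). Response rates: 60% under the alternative and 30% under the null (11.1, 11.4), and at least 50% in preliminary data (4.2.3.1).

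**Assumptions, not in the documents.** The FLT change is roughly normal, its relation to the marker is linear, and the true correlation is 0.4 to 0.6.

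**Step 1: information kept after a yes/no split.** For a normal variable cut so that a proportion p respond, the asymptotic relative efficiency is φ(z_p)² / [p(1 − p)].

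| p | φ(z_p)² | p(1 − p) | Kept | Lost | Effective n from 21 |
|---|---|---|---|---|---|
| 0.5 | 0.1592 | 0.25 | 0.637 | 36% | 13.4 |
| 0.6 | 0.1493 | 0.24 | 0.622 | 38% | 13.1 |
| 0.3 | 0.1209 | 0.21 | 0.576 | 42% | 12.1 |

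The loss is worth 7.6 to 8.9 of the 21 patients.

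**Step 2: power at n = 21.** Simulation: bivariate normal, 60% responders, two-sided 5%, trials kept only if each response level has at least 5 patients.

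| True correlation | Pearson on the change | Logistic, likelihood-ratio test |
|---|---|---|
| 0 | 5% | 6% |
| 0.4 | 44% | 33% |
| 0.5 | 67% | 49% |
| 0.6 | 86% | 69% |

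At correlation 0.5 a rank (Spearman) analysis gives about 59%, so an advantage remains without relying on normality in the test. The logistic test rejects slightly too often when the true correlation is zero, so the gap is not caused by a conservative comparator.

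**Step 3: GR in three levels.** With a latent correlation of 0.5 and an assumed 20/40/40 split across low, intermediate and high, power is about 56% for the FLT change against about 42% for logistic regression. The gap narrows to 14 points.

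**Step 4: the fallback rule.** A trial that reaches 21 patients already has at least 5 responders, because it passed the 11-patient look. The rule can then be triggered only by too few non-responders. Given that 21 patients are reached, the probability of fewer than 5 non-responders is 4% at a true response rate of 60%, 21% at 70% and 59% at 80%. The more often dexamethasone lowers FLT uptake, the likelier it is that the GR question goes untested. A continuous FLT outcome does not need that condition.

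**The case against.** **The plan claims no power here.** Section 11.1 calls these analyses hypothesis-generating, section 11.2 says 21 patients are not powered for every comparison, and section 11.5 says power is not formally justified. No decision rule depends on the GR association. This stands and limits the weight of the point. It does not justify the less informative of two analyses that need the same data.

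**Response is the primary endpoint.** Using it again keeps the paper on one definition. That is a good reason to keep the logistic models as supportive, but not to make them the only GR analysis.

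**The size rests on assumptions.** This also stands. Normality and the correlation are not in the documents, GR may be analysed in three levels, and both approaches are then underpowered. A Wald test would show a wider gap (29% at correlation 0.5), but much of that is small-sample conservatism: it rejects only 2.3% of the time under no association. The SAP names no test, so the Wald figure is not relied on.

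**Stronger readings that the documents do not support.** A reader might infer that the continuous change is ignored for SASP and immune markers too. It is not: sections 2.1, 4.2.3.1 and 11.5 all plan a correlation with it. A reader might also infer that GR is the proposed route to later patient selection. Section 10.2 gives that possible role to FLT-PET; section 4.2.2 explains why patients are not pre-selected on GR in this study, and section 10.3 requires no GR cut-off.

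**Changing the outcome is not enough.** The fallback covers all secondary objectives, and the lesion to be measured is not settled. Both are correct and are dealt with in the fix.

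**Conclusion.** The concern holds in full for GR: secondary objective 3.2(4) is analysed only through the yes/no FLT response. For SASP and immune markers the defect is different: two methods for one question, with neither named as principal.

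Under a roughly normal change, the split costs 36% to 42% of the information. At n = 21 and an assumed correlation of 0.5, this means power of about 49% where 59% (rank) to 67% (Pearson) is available; with three-level GR it is about 42% against 56%. The direction of the loss is secure if the relation is graded, as section 4.2.2 suggests. Its exact size is not, because it depends on the assumed correlation, the distribution of the change and the GR scale.

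The primary endpoint and its decision rule are untouched, and no confirmatory conclusion changes. The plan should still be amended, because the gain is essentially free in a trial meant to inform the next one.

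**What to change.** Amend sections 11.1, 11.4 and 11.5 so that they agree with each other and with sections 2.1 and 4.2.3.1:

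1. **Principal FLT variable.** For GR, SASP and LPFM, use the log ratio of post- to pre-dexamethasone FLT uptake. Name this one scale: percent change and log ratio give the same rank correlation but different linear regressions.
2. **Lesion rule.** Measure it in one target lesion per patient, chosen by a rule fixed in advance. Sections 3.1 (a single target lesion) and 11.1 (any one of the target lesions) must be reconciled first.
3. **Method.** Use rank correlation or linear regression, and state which. Enter GR as an ordinal or quantitative variable and state which of its measurements is used.
4. **Logistic models.** Keep those on responder status as supportive analyses.
5. **Fallback.** Apply the fewer-than-five condition only to analyses with a binary outcome. The 12-patient minimum can stay for all.

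The analyses remain exploratory. The cost is SAP wording and the lesion rule; no further scans, samples or patients are needed.
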